3.6 Stratification Factors and Subgroup Variables

Stratification factors are:

- Tau PET/CSF sampling substudy enrollment (If subjects enrolled in both substudies, subjects will be counted as tau PET substudy)
- Region (US, Australia, Japan, EU < EU countries include France, Germany, Italy, Spain, and Sweden >, Poland)
- Baseline disease stage (MCI or mild AD)
- Baseline AD symptomatic medication use (Yes/No)

All stratification factors are based on subjects' status at PC baseline. A comprehensive list of baseline AD symptomatic medication can be found in PC SAP.

No subgroup analyses will be conducted.

CONFIDENTIAL

The information contained herein may not be used, disclosed, or published without the written consent of Biogen MA Inc.

	Statistical Analysis Plan Long-Term Extension Period	V1.0
---	--	-------------

4 List of Planned Study Analyses

There are two milestone LTE analyses planned for this study: LTE analysis at PC period database lock and the final analysis. The final analysis, which is also known as End of LTE analysis, will only be performed when the LTE study is completed.

4.1 LTE interim analyses at PC period database lock

The LTE interim analyses (IA) will be performed at the PC period database lock after the last patient out in the PC period. All the efficacy analyses described in [Section 5.3](#) will be performed with available efficacy data up to week 104 at the PC period database lock. Given the timeline of scheduled data collection, only a few subjects will have tau PET, CSF biomarker and health outcomes data collected in LTE visits. No LTE analyses of tau PET, biomarker or health outcomes will be included at LTE IA at PC period database lock.

4.2 Final analysis

The LTE analyses will be performed at the end of the LTE period database lock after the last patient out in the LTE period. All the analyses described in [Section 5](#) will be performed with complete data of in the study.

CONFIDENTIAL

The information contained herein may not be used, disclosed, or published without the written consent of Biogen MA Inc.

	Statistical Analysis Plan Long-Term Extension Period	V1.0
---	--	-------------

5 Statistical Methods for Planned Analyses

5.1 General Considerations

Summary tables will be presented using descriptive summary statistics. For continuous variables, summary statistics will generally include: number of subjects with data, mean, standard deviation, median, 25% percentile, 75% percentile, minimum and maximum. For categorical variables, this will generally include: number of subjects randomized or dosed, number with data, and the percent of those with data in each category.

5.2 Study Subjects

The summaries in this section will be based on the FAS. Analysis period will be specified for each table or figure. Unless otherwise specified, summary tables will be presented by LTE treatment group. If not otherwise specified in later text in this SAP, listings will include all data in the placebo-controlled and LTE periods (all data in the study), with an indicator of the study period (pre-dosing, placebo-controlled, or LTE) for each record to indicate when the event occurred. Listings will be presented by LTE treatment group.

5.2.1 Accounting of Subject

Disposition in the LTE period will be summarized for subjects enrolled in LTE. The summary data will include number (%) of subjects randomized and dosed, number (%) of subjects who completed the treatment/study in LTE, and number (%) of subjects who discontinued treatment and/or withdrew from study in LTE. For subjects who discontinued treatment and/or withdrew from study, the reasons for discontinuation and/or withdrawal, days on treatment and days on study in LTE period will be summarized and listed.

Number (%) of subjects who completed the placebo-controlled period but did not enter the LTE period, number (%) of subjects enrolled in LTE (who signed the LTE informed consent) and number (%) of subjects dosed in LTE period will be summarized by LTE treatment group.

5.2.2 Demographics and Baseline Characteristics

Demographics, baseline characteristics, medical history and AD treatment history at PC period baseline will be summarized for subjects enrolled in the LTE period. Please refer to the SAP for the placebo-controlled period.

5.2.2.1 Concomitant Medications and Non-drug Therapies

The number (%) of subjects taking concomitant medication and non-drug therapies in the LTE period will be summarized. In addition, number of subjects in the FAS that have taken any concomitant medications in the placebo-controlled and LTE active treatment period will be summarized.—Concomitant medications and non-drug therapies will be listed for placebo-controlled and LTE period.

CONFIDENTIAL

The information contained herein may not be used, disclosed, or published without the written consent of Biogen MA Inc.

	Statistical Analysis Plan Long-Term Extension Period	V1.0
---	---	-------------

For subjects enrolled in the LTE period, the number (%) of subjects taking AD symptomatic medications concomitantly during the LTE period will be summarized. Please refer to the placebo-controlled SAP for definitions of concomitant therapies and AD symptomatic medication use at baseline.

Disallowed Therapies

Per Section 11.4.1.2 of the Protocol, prohibited and/or restricted medications taken prior to study treatment administration and during the study will be monitored. Disallowed therapies will be reported as Protocol Deviations.

5.2.3 Protocol Deviations

Protocol deviations identified during site monitoring will be captured in a Protocol Deviation log and categorized as major or minor deviations based on Protocol Deviation Classification. The major protocol deviations occurred in the LTE period will be summarized for subjects enrolled in LTE. The major protocol deviations for all FAS subjects in the combined placebo-controlled and LTE periods will also be summarized. Major and minor protocol deviations for all FAS subjects will be listed, respectively, across the placebo-controlled period and the LTE period. Subjects who had incorrect dose assigned by interactive response technology (IRT) in LTE will be summarized and listed. This data will be provided by the unblinded monitors. All summaries for protocol deviations will be presented only by LTE treatment group.

5.2.4 Study Drug Exposure and Study Drug Compliance

A summary table of study drug exposure and compliance in the placebo-controlled and LTE active treatment period will be provided. Number of infusions (BIIB092) received will be summarized as a categorical variable (categories as integers from 1 to 20, and 1-5, 6-10, 11-15, 15-20, 21-26) as well as a continuous variable. Number of weeks on study treatment (BIIB092), calculated as $(\text{date of last dose} - \text{date of first dose} + 1) / 7$, will be summarized as a categorical variable (every 8 weeks from 0 to ≥ 96 weeks) as well as a continuous variable. Percentage of study treatment taken up to the last dose, calculated as $(\text{the actual number of infusions} / \text{by the number of infusions a subject is expected to take until the date of last infusion}) * 100$, will be summarized as a continuous variable. This table will be presented only by LTE treatment group. Similar outputs will also be generated for LTE period.

A listing of study drug administration records will be provided for the combined placebo-controlled and LTE period.

5.2.5 COVID-19 Related Analysis

5.2.5.1 Accounting of subjects who discontinued due to COVID-19

The disposition table due to COVID-19 will be generated for LTE period. The listing of subjects who discontinued treatment and/or withdrew from study due to COVID-19 will be generated for PC and LTE period. Please refer to the placebo-controlled SAP for more details.

CONFIDENTIAL

The information contained herein may not be used, disclosed, or published without the written consent of Biogen MA Inc.

	Statistical Analysis Plan Long-Term Extension Period	V1.0
---	--	-------------

5.2.5.2 Concomitant Non-Drug Treatment for COVID-19

The summary table for the number of subjects using concomitant Non-Drug Treatment for COVID-19 will be summarized for both LTE period and PC and LTE active treatment period. Please refer to the placebo-controlled SAP for more details.

5.2.5.3 COVID-19 Effect on Drug Compliance

Effect of COVID-19 on drug compliance may be assessed for LTE period. Please refer to the placebo-controlled SAP for more details.

5.2.5.4 COVID-19 Protocol Deviation

The table of protocol deviations due to COVID-19 and the summary of impact and reason for major protocol deviations due to COVID-19 will be generated for LTE period. Please refer to the placebo-controlled SAP for more details.

5.2.5.5 Protocol Alternation Due to COVID-19cx

Protocol alternation due to COVID-19 will be listed for PC and LTE period. Please refer to the placebo-controlled SAP for more details.

5.3 Efficacy Analysis

5.3.1 General Considerations

The analysis population for efficacy analysis is the same as the FAS and data from both the placebo-controlled and LTE periods will be include. All efficacy analyses will be presented by study treatment groups as defined in Section 3.3. The early start high-dose subjects are the subjects who were randomized to high-dose BIIB092 group in the PC period, and the late start high-dose subjects are the subjects who were randomized to Placebo in the PC period, regardless of enrollment of the LTE period or not.

The following comparison will be evaluated for the long-term efficacy of BIIB092:

- The early start high dose compared with the late start high dose.

The comparisons between low-dose and late start high dose, and middle-dose and late start high dose might be conducted. There will be no multiple comparison adjustments.

Visit windows for mapping efficacy endpoint

For efficacy data that are summarized by visit, assessment from all scheduled visits, EOS visit and unscheduled visits will be mapped to an appropriate analysis visit using a windowing scheme ([Appendix I](#)).

CONFIDENTIAL

The information contained herein may not be used, disclosed, or published without the written consent of Biogen MA Inc.

	Statistical Analysis Plan Long-Term Extension Period	V1.0
---	--	-------------

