Note: The study comprises a double-blind, placebo-controlled period and an LTE period. The total duration for participants who complete the placebo-controlled period and do not enter the LTE period will be approximately 99 weeks. The total study duration for participants who complete both the placebo-controlled period and the LTE period will be approximately 247 weeks. The double-blind placebo-controlled period comprises a Screening Period of up to approximately 9 weeks (65 days), a Treatment Period of 76 weeks, and for participants not entering the LTE period, an End of Study EOS Visit at Week 78, and a Follow-up Safety Visit at Week 90, or approximately 14 weeks after the last dose of study treatment. The LTE period comprises an LTE Screening Period of approximately 4 weeks starting at Week 76, a 144-week Treatment Period starting at Week 80, an EOS Visit at Week 226, and a Follow-up Safety Visit at Week 238, or approximately 14 weeks after the last dose of study treatment.

CONFIDENTIAL

The information contained herein may not be used, disclosed, or published without the written consent of Biogen MA Inc.

Rationale: To date, BIIB092 has been generally well tolerated in the clinical study participants. There are no important identified or important potential risks in the program, including in the completed studies CN002001 and CN002003 and in the ongoing studies 251PP201, 251PP301, and 251AD201. The current safety profile supports continued investigation of the proposed doses of 125 to 2000 mg. The LTE will provide additional long-term safety data.

Switching all participants who received placebo during the placebo-controlled period to 1 group (2000 mg every 4 weeks) in the LTE period allows delayed start analysis to be maximized for 1 of the dose groups.

This change also affects Section 5, Schedule of Activities (addition of 3 new tables for the LTE period); Section 6, Study Objectives and Endpoints; Section 7.2, Study Duration for Participants; [REDACTED] addition of Section 8.3, Inclusion Criteria for Long-Term Extension Period and Section 8.4, Exclusion Criteria for Long-Term Extension Period; Section 9.1 Screening; Section 9.2, Randomization; Section 9.3, Blinding Procedures; Section 10.1, Discontinuation of Study Treatment; Section 11.1, Regimen; Section 11.5, Continuation of Treatment; Section 13.6, Immunogenicity; and Section 16, Statistical Methods and Determination of Sample Size.

CONFIDENTIAL

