3.3 Study Treatment

For efficacy and health outcome analyses, the following LTE treatment groups of BIIB092 (per randomization) will be evaluated:

- low-dose (BIIB092 -125mg once every 4weeks or 375mg once every 12weeks)

CONFIDENTIAL

The information contained herein may not be used, disclosed, or published without the written consent of Biogen MA Inc.

	Statistical Analysis Plan Long-Term Extension Period	V1.0
---	---	-------------

- medium-dose (BIIB092 - 600mg once every 4 weeks)
- early start high-dose (BIIB092 - 2000mg once every 4 weeks)
- late start high-dose (BIIB092 - 2000mg once every 4 weeks)

For other analyses, such as safety, PK, PD, biomarker, and anti-drug antibody analyses, low dose group will be split out for different frequencies. The following LTE treatment groups of BIIB092 will be evaluated:

- low-dose 125mg once every 4weeks
- low-dose 375mg once every 12weeks
- medium-dose (BIIB092 - 600mg once every 4 weeks)
- early start high-dose (BIIB092 - 2000mg once every 4 weeks)
- late start high-dose (BIIB092 - 2000mg once every 4 weeks)

Since subjects in low-dose group and medium-dose group are taking the same treatment from the start of placebo-controlled period to the end of LTE period, so the subjects in these treatment groups are all considered as early start subjects. Late start subjects refer to subjects who were on placebo during placebo-controlled period then switched to high-dose (BIIB092 - 2000mg once every 4 weeks). Throughout this SAP, these study treatment schemes will be referred as LTE treatment.

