5.3.2 Method of Analysis

5.3.2.1 Considerations for base MMRM model for change from baseline analyses

A mixed model with repeated measures (MMRM) will be used to analyze changes from baseline in a parameter of interest using fixed effects of LTE treatment group, visit (categorical), LTE treatment group-by-visit interaction, baseline of the parameter of interest, baseline of the parameter of interest-by-visit interaction, region (Japan and Australia will be combined), baseline MMSE, baseline disease stage, and baseline AD symptomatic medication use. The correlation between repeated measures of the outcomes will be taken into consideration. An unstructured covariance matrix will be used to model the within-subject variance-covariance errors. If the unstructured covariance structure matrix results in a lack of convergence, the heterogeneous first-order autoregressive covariance structure followed by the heterogeneous Toeplitz covariance structure will be used. The least-squares (LS) means, the differences in LS means between each LTE treatment group versus placebo at each visit, 95% confidence intervals (CIs), and p-values will be presented. In the primary analysis of each endpoint, missing data are assumed to be missing at random [Rubin 1976].

For the LTE interim analysis at PC DBL, only records up to week 104 will be included in the MMRM model.

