5.3.3 Primary Efficacy Endpoint

Estimand 1 (treatment policy strategy): The difference in change from baseline CDR-SB scores in subjects assigned to BIIB092 group in the PC period, comparing to late start BIIB092 group, regardless what actual treatment is received acknowledging a participant may miss more than four infusions, consecutively, change AD symptomatic medication and/or discontinue treatment early

- Analysis set: all subjects in the FAS
- Variable: The change from baseline CDR-SB scores at the week of interest regardless of intercurrent events (ICEs)
- Analysis set level summary: Least square (LS) mean difference from MMRM model in change from baseline between BIIB092 and placebo
- ICEs and Strategies for Addressing ICEs:

ICEs include

- AD symptomatic medication change (treatment policy strategy)
- Treatment discontinuation (treatment policy strategy)
- Missing more than or equal to four infusions consecutively (treatment policy strategy)

Since a treatment policy strategy will be used for all ICEs in this estimand, all observed data will be included regardless of miss more than or equal to four infusions consecutively, treatment discontinuation or AD symptomatic medication change. At LTE interim analysis, the primary

CONFIDENTIAL

The information contained herein may not be used, disclosed, or published without the written consent of Biogen MA Inc.

	Statistical Analysis Plan Long-Term Extension Period	V1.0
---	--	-------------

analysis is the mean difference of the change from baseline CDR-SB scores at Week 104 between treatment groups in the FAS who have a baseline and at least one post-baseline CDR-SB score [ICH E9 (R1) Addendum 2014, 2017]. At final analysis, the primary analysis is the mean difference of the change from baseline CDR-SB scores at the week of interest between treatment groups in the FAS who have a baseline and at least one post-baseline CDR-SB score. All observed data will be included in the primary analysis, including data collected after intercurrent events [ICH E9 (R1) Addendum 2017], i.e., treatment discontinuation or a change in concomitant use of AD symptomatic medication

The baseline and change from baseline CDR-SB scores at each post-baseline visit will be summarized by LTE treatment group. A mixed model with repeated measures (MMRM) will be used to analyze changes from Baseline in CDR-SB as described in [Section 5.3.2.1](#). A line plot of adjusted mean change from baseline over time will be provided.

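### After Week 80, the LTE contrasts of low and medium dose with the former placebo arm measure neither dose nor delayed start, and will tend to understate a lower dose's benefit

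*SAP*

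**What the plan says.** SAP 3.3 defines the comparator: "Late start subjects refer to subjects who were on placebo during placebo-controlled period then switched to high-dose" (2000 mg every 4 weeks, from Week 80). Three efficacy passages then describe who is compared with it, and they do not agree.

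- **SAP 5.3.1** names one comparison to be evaluated: "The early start high dose compared with the late start high dose". It makes the others conditional: "The comparisons between low-dose and late start high dose, and middle-dose and late start high dose might be conducted". No multiplicity adjustment is planned.
- **SAP 5.3.2.1** is not conditional: "the differences in LS means between each LTE treatment group versus placebo at each visit, 95% confidence intervals (CIs), and p-values will be presented". No LTE group is on placebo after Week 80.
- **SAP 5.3.3**, Estimand 1, covers the difference "in subjects assigned to BIIB092 group in the PC period, comparing to late start BIIB092 group". It is not limited to the high dose. Its summary measure names placebo as the comparator, and the final-analysis timepoint is an unspecified week of interest.

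SAP 5.3.4 applies the same model to ten exploratory endpoints. SAP 4.1 runs all the efficacy analyses at the LTE interim, with data to Week 104. Nothing limits the low- and medium-dose contrasts to visits through Week 78 or says how to read later ones.

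The Version 3 amendment summary in the protocol, explaining why all placebo participants switch to 2000 mg, says that this "allows delayed start analysis to be maximized for 1 of the dose groups".

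**The concern.** Early-start and late-start 2000 mg share a dose after Week 80 and differ only in when treatment began, so their difference is a clean delayed-start contrast. Low- and medium-dose participants differ from the late-start group in two ways that can pull in opposite directions: they started earlier, but from Week 80 they receive less drug than their comparator. One number nets the two and identifies neither.

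If 2000 mg works, the comparator's decline slows after the switch, so a lower dose's contrast falls short of its benefit against no treatment even if that dose keeps working unchanged. Printed with a p-value under a placebo label, the shortfall could be read as waning or absence of effect at the lower dose. Protocol 4.4 says the study should help inform dose selection.

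**Working it through.** **The plan's own figure.** The LTE SAP gives no power for these contrasts. Protocol 16.10 gives approximately 80% power for dose-response at Week 78. Its inputs are a placebo change of 1.99, SD 2.38, 40% reduction at the highest dose, 20% dropout, planned arms 88/88/176/176 and two-sided 5%. For 2000 mg versus placebo, n = 176 × 0.8 = 140.8 per arm and the difference is 0.4 × 1.99 = 0.796. Then 0.796 / (2.38 × √(2/140.8)) = 2.81, and Φ(2.81 − 1.96) = 80.1%. A simulation of MCP-MOD with six assumed shapes (the Figure 2 parameters are not visible) gave 80.8% to 85.4%. The inputs therefore reproduce the stated figure.

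**Expected contrast after Week 80.** Assumptions not in the documents: decline stays linear beyond Week 78, slowing is a constant proportion, it starts at once on dosing, and every placebo participant enters the LTE.

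- Slope s = 1.99/78 = 0.0255 points per week.
- Early group with slowing r: change at week w = s·w·(1 − r).
- Late-start group: s·[80 + 0.6·(w − 80)].
- Contrast = −s·[r·w − 0.4·(w − 80)]; negative favours the early group.
- Effect against no treatment = −s·r·w.
- Gap between the two = 0.4·s·(w − 80), whatever r is: 0.245 at Week 104, 0.490 at Week 128, 0.735 at Week 152.

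At Week 104:

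| Slowing r | Basis | Contrast with late start | Against no treatment |
|---|---|---|---|
| 2.5% | low dose, linear: 125/2000 × 40% | +0.18 | −0.07 |
| 10% | assumed | −0.02 | −0.27 |
| 12% | medium dose, linear: 600/2000 × 40% | −0.07 | −0.32 |
| 20% | assumed | −0.29 | −0.53 |
| 30% | assumed | −0.55 | −0.80 |
| 37.5% | in proportion to tau suppression: 91/97 × 40% | −0.75 | −1.00 |
| 40% | early-start 2000 mg | −0.82 | −1.06 |

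Linear is one of the candidate shapes in Protocol 16.4.2.1. The suppression figures are from the earlier multiple-dose study in PSP (Protocol 4.3.2; 150 mg against 2100 mg).

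For 20% slowing the shortfall is 0.245/0.531 = 46% of the effect; for 12% it is 0.245/0.318 = 77%. In the last row the contrast is −0.82 at every LTE visit, which is the pure delayed-start effect.

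**Change of sign.** The contrast turns positive when r < 0.4·(w − 80)/w: 9.2% at Week 104, 15.0% at Week 128, 18.9% at Week 152.

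**Precision.** With 88 × 0.8 = 70.4 against 140.8 and SD held at 2.38, SE = 2.38 × √(1/70.4 + 1/140.8) = 0.35. The Week 104 gap of 0.245 is about 0.7 SE. For a dose with 20% slowing, the chance of a significant favourable result falls from 21% at Week 78 to 13% at Week 104.

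**Incomplete LTE entry.** If only 60% of the former placebo arm enters and the rest are counted at the untreated rate, the gap scales by 0.6. The Week 104 contrasts become −0.38 (20% slowing) and −0.17 (12% slowing).

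**Dose contrast with the same start.** Under the linear shape, medium minus early-start 2000 mg at Week 104 is s × 104 × (0.40 − 0.12) = +0.74, at the same planned SE of 0.35.

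**The case against.** The strongest points on the other side:

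- *The plan barely commits to these contrasts.* This is true of SAP 5.3.1, where they are optional. It does not survive SAP 5.3.2.1, which says the differences will be presented for every group at every visit.
- *Nothing is confounded in the usual sense.* This stands. A reader might infer that randomisation is broken, but participants are analysed as randomised. Low or medium dose from Day 1, compared with placebo then 2000 mg, is a valid comparison of two sequences and fits a treatment-policy estimand. What fails is reading it as a dose, delayed-start or placebo effect.
- *A reader might infer that an effective lower dose would look harmful.* The documents do not support that as the expected outcome. At Week 104 only the 2.5% case reverses, by about half an SE. The same formula gives +0.34 at Week 226 for 20% slowing, but SAP 5.6.2 says no participant reached Week 226. The top infusion category in SAP 5.2.4 is 21–26; with 20 infusions through Week 76, the 26th falls at Week 100, which suggests (an inference) little data much later. A nearly flat dose-response, as the tau suppression figures would imply, gives no reversal.
- *Dose selection does not rest on the LTE.* This largely stands. The formal dose-response analysis is MCP-MOD at Week 78 and is untouched. LTE efficacy is exploratory, and Protocol 16.1 plans descriptive statistics for it.
- *Contrasts through Week 78 belong to the separate placebo-controlled SAP.* True, but that is a reason to stop treating them as efficacy contrasts here after that visit.

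**Conclusion.** The point holds as a problem of interpretation and of inconsistent specification. After Week 80 the low- and medium-dose contrasts with the former placebo arm compare treatment sequences. They cannot be read as effects against placebo, as delayed-start effects or as dose effects. The committed early versus late 2000 mg contrast is sound.

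The realistic consequence is attenuation: about 0.25 CDR-SB points at the Week 104 interim if 2000 mg slows decline by 40%, whatever the lower dose's own effect. This is below one standard error, so no single contrast would be decisive either way. The size rests on linear decline, immediate onset, full LTE entry, the planned allocation (654 were randomised against 528 planned) and an SD fixed at 2.38. Incomplete entry dilutes the distortion, and a smaller effect at 2000 mg would shrink it. Reversal needs a dose much weaker than 2000 mg, or longer follow-up than the data appear to offer.

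**What to change.** 1. Reconcile SAP 5.3.1, 5.3.2.1 and 5.3.3 so that early-start versus late-start 2000 mg is the only delayed-start contrast after Week 80, and state this in Estimand 1.
2. Treat low and medium dose versus the former placebo arm as efficacy contrasts only through Week 78. Label any later ones as treatment-sequence comparisons and remove the placebo label.
3. Add low and medium dose versus early-start 2000 mg as the dose contrast in the LTE. It is randomised, with the same start time, and comes from the same model.

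The cost is SAP wording and changed contrast statements; no new data or model are needed. The early-start and late-start 2000 mg groups have the same planned size (176 each), so planned precision is unchanged, although actual LTE numbers depend on entry. The one loss is that later low- and medium-dose differences from the former placebo arm are no longer reported as efficacy tests.
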